4.3 JUSTIFICATION FOR DOSE

Subjects randomized to CO will be administered algorithm-specified iCO dose (not to exceed 500 ppm) to achieve a COHb of 6-8% for up to 90 minutes for three consecutive days. The decision to target a COHb level of 6-8% is based on animal studies demonstrating protection in sepsis and ALI models (**Table 1**)^{24-26,28,30,32,33,38,45-55} and human studies demonstrating safety (**Table 2**)^{35,101,104,105,107,108,129} at these COHb levels.

Given diffusion impairment in patients with ARDS, it is anticipated, based on CFK equation predictions (**Table 4**), that subjects will require doses in the range of 200-500 ppm to achieve COHb levels of 6-8%. The decision to limit the maximal dose to 500 ppm is based on concern for potential epithelial toxicity at inhaled concentrations above 500 ppm. Previous studies have demonstrated safety of CO inhalation at 500 ppm in humans¹⁰⁵ and reduction of pulmonary neutrophilia in non-human primates⁵⁴, therefore we do not anticipate epithelial toxicity at our maximal dose.

The rationale for once-daily dosing as opposed to continuous inhalation, as with inhaled NO or other pulmonary vasodilators, is based on pre-clinical studies showing that CO treatment for short periods of time induces transcriptional programs of mitochondrial biogenesis^{36,40,41,130} and induces autophagy^{33,39,40,131-133} leading to downstream protection without the need for continuous inhalation. In addition, prior work from our group demonstrated safety and activation of mitochondrial biogenesis in healthy individuals after three consecutive days of treatment^{10,35}. Once-daily iCO dosing will also optimize subject safety by ensuring that COHb levels do not exceed our target range of 6-8%, and that CO accumulation will not occur as treatments are separated by 4-6 half-lives for CO elimination¹³⁴⁻¹³⁶.

4.4 END OF STUDY DEFINITION

A participant is considered to have completed the study if he or she has completed all phases of the study including the last visit or the last scheduled procedure shown in the Schedule of Activities (SoA), **Section 1.3**. The end of the study is defined as completion of the last visit or procedure shown in the SoA in the trial globally.

5 STUDY POPULATION

5.1 INCLUSION CRITERIA

All patients (age 18 and older) will be eligible for inclusion if they meet all of the following consensus criteria for sepsis and ARDS^{3,4} or if they meet the criteria for pneumonia as described below.

- Patients with sepsis are defined as those with life-threatening organ dysfunction caused by a dysregulated host response to infection:
 1. Suspected or proven infection: Sites of infection include thorax, urinary tract, abdomen, skin, sinuses, central venous catheters, and central nervous system
 2. Increase in Sequential Organ Failure Assessment (SOFA) Score ≥ 2 over baseline
- ARDS is defined when all four of the following criteria are met:
 1. A $\text{PaO}_2/\text{FiO}_2$ ratio ≤ 300 with at least 5 cm H₂O positive end-expiratory airway pressure (PEEP)
 2. Bilateral opacities on frontal chest radiograph (not fully explained by effusions, lobar/lung collapse, or nodules) within 1 week of a known clinical insult or new or worsening respiratory symptoms
 3. A need for positive pressure ventilation by an endotracheal or tracheal tube
 4. Respiratory failure not fully explained by cardiac failure or fluid overload; need objective assessment (e.g., echocardiography) to exclude hydrostatic edema if no risk factor is present
- Pneumonia (without ARDS or sepsis) will be defined as a unilateral or bilateral lung infiltrate on chest X-ray or chest CT (not fully explained by effusions, lobar/lung collapse or nodules) in the setting of receiving mechanical ventilation, a new suspected respiratory infection, an increase in SOFA score less than 2 at the time of randomization (baseline).
- Pneumonia (with sepsis, without ARDS) will be defined as a unilateral or bilateral lung infiltrate on chest X-ray or chest CT (not fully explained by effusions, lobar/lung collapse or nodules) in the setting of receiving mechanical ventilation and a new suspected respiratory infection with an increase in SOFA score of ≥ 2 over baseline at the time of randomization. Pneumonia with bilateral opacities, $\text{PaO}_2/\text{FiO}_2$ ratio ≤ 300 , or an increase in SOFA score greater than or equal to 2 over baseline will continue to be considered ARDS and sepsis.

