NYHA: New York Heart Association Class IV subjects (defined as subjects who have cardiac disease resulting in inability to carry out physical activity without discomfort. Symptoms of cardiac insufficiency or an anginal syndrome may be present even at rest. If any physical activity is undertaken, discomfort is increased).

Pneumonia: Unilateral or bilateral pulmonary infiltrates in a patient with suspected respiratory infection.

Sepsis: Life-threatening organ dysfunction caused by a dysregulated host response to infection:

1. Suspected or proven infection: Sites of infection include thorax, urinary tract, abdomen, skin, sinuses, central venous catheters, and central nervous system.
2. Increase in SOFA score greater than or equal to 2 over baseline.

Study Drug: Defined as inhaled carbon monoxide or placebo.

Study hospital: Defined as the hospital where the patient was enrolled.

Study withdrawal: Defined as permanent withdrawal from study before completion of study activities.

This does not include those subjects who have completed the protocol procedures or stopped procedures because they have reached unassisted breathing. If a patient or surrogate requests withdrawal from the study, the investigators will seek explicit permission to continue data collection.

UAB (Unassisted Breathing): Spontaneously breathing with face mask, nasal prong oxygen, or room air, T-tube breathing, tracheostomy mask breathing, or CPAP ≤ 5 without PS or IMV assistance, or the use of noninvasive ventilation solely for sleep-disordered breathing. Assisted breathing is any level of ventilator support at pressures higher than the unassisted breathing.

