8.3 RANDOMIZATION PROCEDURES (DAY 0)

8.3.1 RANDOMIZATION

All ARDS criteria (for those enrolled with sepsis-induced ARDS) and pneumonia criteria in ventilated patients must occur within the same 24 hour period. The onset of ARDS is when the last criterion is met. Patients must be enrolled within 168 hours of ARDS onset or diagnosis of pneumonia in a ventilated patient. Information for determining when these time window criteria were met may come from either the site hospital or reports from a referring hospital.

Following randomization, the low tidal volume protocol for mechanical ventilation must be initiated within two hours for those subjects with ARDS..

The first treatment of study drug should be given within 24 hours of randomization. The day of randomization will be considered study day zero.

Eligible participants will be randomized to one of the two treatment arms using a permuted block method¹⁴⁶ with random block sizes. The randomization ratio will be 2:1 iCO:placebo. The randomization will not be stratified by any factors. The study biostatistician will verify all the necessary randomization information (blinding method, randomization method, block size, and number of treatment groups) in the StudyTRAX randomization configuration module.

Site investigators will review all potential study participants with one of the CCC physician members. Following informed consent, the unblinded administering RT or physician or blinded study coordinator will randomize subjects in the database using the StudyTRAX randomization tool. The unblinded administering RT or physician will obtain the subject's treatment assignment through the "View Treatment" button in the blinded database, a privilege granted to unblinded RTs and physicians only. CO-

related measurements (SpCO, COHb, ambient CO) and drug-related information will be in a separate project within the database, which the blinded study coordinators will not have access to. This central review of randomization by the CCC unblinded physician will ensure that no subjects are enrolled in this multi-center trial during planned or unplanned study holds.

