9 STATISTICAL CONSIDERATIONS

9.1 STATISTICAL HYPOTHESES

Hypothesis: We hypothesize that low dose iCO will be safe and well-tolerated and that the CFK equation-based iCO personalized dosing algorithm will be accurate in achieving a target COHb level of 6-8% in patients pneumonia (without ARDS and sepsis or with sepsis without ARDS criteria) and with sepsis-induced ARDS at study entry.

We further hypothesize that precision-based iCO therapy will reduce the severity of pneumonia and ARDS and organ failure by suppressing mitochondrial dysfunction, inhibiting inflammasome activation and necroptosis, and accelerating resolution of inflammation.

Primary Endpoints:

1. The primary endpoint is **safety of iCO**, defined by the incidence of pre-specified administration-related AEs and SAEs.

Administration-related SAEs are: 1) myocardial infarction; 2) stroke; 3) new onset arrhythmia requiring DC cardioversion; 4) worsening hypoxemia^{1,2}; 5) COHb \geq 10%; and 6) increase in lactate by \geq 2 mmol/L.

2. **Accuracy** of the CFK equation-based personalized iCO dosing algorithm to achieve a COHb level of 6-8%.

Secondary Endpoints:

1. Lung Injury Score (LIS) on days 1-5 and day 7
2. PaO₂/FiO₂ ratio on days 1-5 and day 7
3. Oxygenation index (OI) on days 1-5, and 7
4. Dead space fraction (Vd/Vt) on days 1-3 and day 7
5. Sequential Organ Failure Assessment (SOFA) scores on days 1-5, 7, 14, and 28
6. Ventilator-free days at day 28
7. ICU-free days at day 28
8. Hospital-free days to day 60
9. Hospital mortality to days 28 and 60
10. Neurocognitive function at 3 and 6 months

Exploratory Endpoints:

1. Plasma and urine biomarkers of mitochondrial dysfunction (mtDNA)
2. Plasma and urine biomarkers of inflammasome activation (IL-18)
3. Plasma and urine biomarkers of necroptosis (RIPK3)
4. Plasma Lipid mediators (LM) and specialized pro-resolving mediators (SPMs)

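### The last sentence of 5.1 says 'or' where the definitions need 'and': read literally, it empties one of the three entry-criteria groups that 9.4 analyses (minor correction)

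*Combined protocol and SAP*

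**What the plan says.** Under 5.1 a patient qualifies either by meeting the sepsis and ARDS criteria in full or by meeting a pneumonia definition. The building blocks are:

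- **ARDS (5.1):** "ARDS is defined when all four of the following criteria are met". The four are PaO2/FiO2 of 300 or less with PEEP of at least 5 cm H2O, bilateral opacities, positive pressure ventilation through a tube, and respiratory failure not fully explained by a cardiac cause or fluid overload.
- **Sepsis (5.1, repeated in 1.4):** infection plus "Increase in SOFA score greater than or equal to 2 over baseline".
- **Pneumonia without either (5.1):** "Pneumonia (without ARDS or sepsis) will be defined as a unilateral or bilateral lung infiltrate on chest X-ray or chest CT", with a SOFA increase below 2.
- **Pneumonia with sepsis only (5.1):** "Pneumonia (with sepsis, without ARDS) will be defined as a unilateral or bilateral lung infiltrate on chest X-ray or chest CT", with a SOFA increase of 2 or more.

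The section then closes by saying that pneumonia with bilateral opacities, PaO2/FiO2 of 300 or less, "or an increase in SOFA score greater than or equal to 2 over baseline will continue to be considered ARDS and sepsis". This is operative text; it does not stand only in the summary of changes.

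Section 9.1 states the study population as "pneumonia (without ARDS and sepsis or with sepsis without ARDS criteria) and with sepsis-induced ARDS at study entry". Sections 9.4.2, 9.4.3 and 9.4.5 turn these groups into a factor with three levels: ARDS/Sepsis, Non-ARDS/Sepsis Pneumonia and Non-ARDS/non-Sepsis Pneumonia.

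**The concern.** The closing sentence of 5.1 undoes the definition just before it. A SOFA increase of 2 or more is the entry ticket to the pneumonia-with-sepsis group, and through 'or' it is also sufficient on its own to relabel the patient as ARDS and sepsis. The other two triggers misfire as well. Both pneumonia definitions expressly allow bilateral infiltrates, yet bilateral opacities alone would count as ARDS. A patient with a low PaO2/FiO2 but a SOFA increase below 2 would be called septic.

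Section 9.4 names the levels of the entry-criteria factor but gives no rule for coding it, and no text says which part of 5.1 prevails. A coder who followed the closing sentence would find the middle level empty and the ARDS/Sepsis level mixed with pneumonia that is not ARDS.

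**Working it through.** The plan gives no figure to reproduce; the check is logical.

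**Inputs (all from 5.1).** For a ventilated pneumonia patient let B = bilateral opacities, P = PaO2/FiO2 of 300 or less, S = SOFA increase of 2 or more. To keep the table small, PEEP of at least 5 cm H2O and ARDS criterion 4 are taken as met, so ARDS = B and P, and sepsis = S.

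**Direct argument.** The middle group is pneumonia with S and without ARDS. The closing sentence relabels pneumonia with (B or P or S). S implies (B or P or S), so every member of the middle group is relabelled and 0 remain. This step needs no assumption about PEEP, criterion 4, patient mix or any link between P and S.

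**All 2 × 2 × 2 = 8 profiles.**

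| B | P | S | By the ARDS and sepsis definitions | By the closing sentence |
|---|---|---|---|---|
| no | no | no | Non-ARDS/non-Sepsis | Non-ARDS/non-Sepsis |
| no | no | yes | Non-ARDS/Sepsis | ARDS/Sepsis |
| no | yes | no | Non-ARDS/non-Sepsis | ARDS/Sepsis |
| no | yes | yes | Non-ARDS/Sepsis | ARDS/Sepsis |
| yes | no | no | Non-ARDS/non-Sepsis | ARDS/Sepsis |
| yes | no | yes | Non-ARDS/Sepsis | ARDS/Sepsis |
| yes | yes | no | ARDS without sepsis: no level named | ARDS/Sepsis |
| yes | yes | yes | ARDS/Sepsis | ARDS/Sepsis |

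- Literal 'or': 7 profiles are ARDS/Sepsis, 0 are Non-ARDS/Sepsis, 1 is Non-ARDS/non-Sepsis. Of the 7, only 1 meets both definitions.
- Definitions: 1 ARDS/Sepsis, 3 Non-ARDS/Sepsis, 3 Non-ARDS/non-Sepsis, and 1 with no level (1 + 3 + 3 + 1 = 8).

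These are counts of profiles, not of patients. Some profiles may be rare, since SOFA itself uses PaO2/FiO2 (8.1).

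**A kinder parse.** Read the sentence as B and (P or S). Unilateral septic pneumonia then stays in the middle group (2 profiles). But bilateral disease with PaO2/FiO2 above 300 and S becomes ARDS, against the four-criterion rule, and bilateral disease with P but a SOFA increase below 2 becomes septic, against the sepsis definition. This parse does not agree with the definitions either.

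**Effect on the models.** With three levels, the entry-criteria main effect has 3 − 1 = 2 degrees of freedom, and treatment by entry criteria has (2 − 1)(3 − 1) = 2. With three days, the three-way term has (2 − 1)(3 − 1)(3 − 1) = 4. With the middle level empty these fall to 1, 1 and 2, and no contrast involving that level can be estimated.

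**The case against.** The best defence is that the intent is plain. The lead-in of 5.1 asks for the sepsis and ARDS criteria in full, ARDS is defined by all four criteria, and the closing sentence says such patients *continue* to be classed that way, which points back to the existing definition and announces no new one. Each group's name carries its own boundary, 9.1 repeats the groups, and 9.4 does not say that the factor is coded from the closing sentence. A statistician reading the whole document would probably code the intended groups.

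Most of that stands, and it is why the point is minor. It does not make the sentence right: neither reading of 'or' examined above fits both the four-criterion rule and the pneumonia definitions, and 9.4 supplies no coding rule to fall back on.

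Some stronger inferences are not supported:

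- *That many separate passages demand 'and'.* The sepsis definitions contradict the sentence but do not join SOFA to opacities or oxygenation. The 8.3.1 rules, "All ARDS criteria (for those enrolled with sepsis-induced ARDS) and pneumonia criteria in ventilated patients must occur within the same 24 hour period" and "The onset of ARDS is when the last criterion is met", concern timing and presuppose the ARDS definition. The direct support is that definition, the 5.1 lead-in and the groups in 9.1.
- *That patients have been or will be mislabelled in some number.* The documents give no patient mix and do not tie the coding to this sentence.
- *That the primary safety result is at risk.* The affected COHb model is a repeat of the main one with a factor added. The interaction in 9.4.3 is declared exploratory and unpowered, and the within-group analyses are post-hoc and hypothesis-generating.

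**Conclusion.** The point holds as a minor error of wording in a classification rule. Applied as written, the closing sentence of 5.1 leaves 1 of the 3 entry-criteria levels with 0 members and places non-ARDS pneumonia in the ARDS/Sepsis level. The zero follows from the wording alone. The profile counts also assume that PEEP and ARDS criterion 4 are met.

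**Affected:** the repeat 90-minute COHb ANOVA with entry criteria and its interactions (9.4.2, 9.4.5), the exploratory treatment-by-entry-criteria term, and the post-hoc within-group analyses (9.4.3).

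**Not affected:** the first COHb ANOVA (treatment, time and their interaction), adverse-event incidence, the comparison of COHb of 10% or more, predicted-versus-measured COHb, allocation (unstratified, 6.3) and the sample size of 36 (9.2). How many of the 36 would be mislabelled cannot be calculated from the documents.

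**What to change.** 1. In 5.1, replace the closing sentence with: *Pneumonia that meets all four ARDS criteria and also has a SOFA increase of 2 or more over baseline is classed as ARDS and sepsis.*
2. In 9.4, add a coding rule. Pneumonia that does not meet all four ARDS criteria is Non-ARDS/Sepsis if the SOFA increase is 2 or more, and Non-ARDS/non-Sepsis if it is below 2.
3. State the level, or the ineligibility, of pneumonia that meets all four ARDS criteria with a SOFA increase below 2. Changing 'or' to 'and' does not settle this profile: it is ARDS without sepsis, and none of the three levels describes it.
4. Code the factor from data at study entry, using the investigator's eligibility judgement for ARDS criterion 4.

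The cost is one sentence in 5.1 and a short paragraph in 9.4. The qualifying radiograph, the qualifying blood gas, ventilator parameters and SOFA are already on the 8.4 baseline list. A reader might infer that nothing further needs recording, but criterion 4 is not on that list and is not required on the pneumonia route. The investigator's judgement on it should therefore be recorded for pneumonia patients who meet the other three criteria.

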5.2 EXCLUSION CRITERIA

An individual who meets any of the following criteria will be excluded from participation in this study:

1. Age less than 18 years
2. Greater than 168 hours since ARDS or pneumonia with mechanical ventilation onset
3. Pregnant or breastfeeding
4. Prisoner

5. Patient, surrogate, or physician not committed to full support (exception: a patient will not be excluded if he/she would receive all supportive care except for attempts at resuscitation from cardiac arrest)
6. No consent/inability to obtain consent or appropriate legal representative not available
7. Physician refusal to allow enrollment in the trial
8. Moribund patient not expected to survive 24 hours
9. No arterial line or central line/no intent to place an arterial or central line
10. No intent/unwillingness to follow lung protective ventilation strategy for subjects with ARDS
11. Severe hypoxemia defined as $\text{SpO}_2 < 95$ or $\text{PaO}_2 < 90$ on $\text{FiO}_2 \geq 0.9$
12. Hemoglobin < 7.0 g/dL
13. Subjects who are Jehovah's Witnesses or are otherwise unable or unwilling to receive blood transfusions during hospitalization
14. Acute myocardial infarction (MI) or acute coronary syndrome (ACS) within the last 90 days
15. Coronary artery bypass graft (CABG) surgery within 30 days
16. Angina pectoris or use of nitrates with activities of daily living
17. Severe cardiopulmonary disease classified as New York Heart Association (NYHA) class IV
18. Stroke (ischemic or hemorrhagic) within the prior 1 month, cardiac arrest requiring CPR within the prior 72 hours, or inability to assess mental status following cardiac arrest
19. Burns > 40% total body surface area
20. Severe airway inhalational injury
21. Use of high frequency oscillatory ventilation
22. Use of extracorporeal membrane oxygenation (ECMO)
23. Use of inhaled pulmonary vasodilator therapy (eg. nitric oxide [NO] or prostaglandins)
24. Diffuse alveolar hemorrhage from vasculitis
25. Concurrent participation in other investigational drug study

Reasons for Exclusions:

Patients less than 18 years of age are excluded because the participating ICUs do not typically admit pediatric patients and we believe the benefit/risk ratio for children to receive iCO is not appropriate at this early stage. Patients with ARDS or pneumonia with mechanical ventilation for more than 168 hours are excluded in order to evaluate more clearly the effects of iCO early in the course of lung injury. Patients with severe hypoxemia or need for ECMO are excluded because they may not have adequate reserve to tolerate the reduction in oxygen carrying capacity. The parameters of $\text{SpO}_2 < 95$ or $\text{PaO}_2 < 90$ on $\text{FiO}_2 \geq 0.9$ are used rather than a simpler $\text{PaO}_2/\text{FiO}_2$ ratio of 100 to define severe hypoxemia for both enrollment and daily treatment to better account for factors affecting arterial oxygen content and to ensure an additional safety margin during treatment of enrolled subjects. These criteria exclude patients with $\text{PaO}_2/\text{FiO}_2 \leq 100$ ($\text{PaO}_2 90/\text{FiO}_2 0.9$), but also explicitly specify a safety margin of 0.1 for FiO_2 . These criteria are currently approved by the Institutional Review Boards (IRBs) at our participating clinical centers, our DSMB, and the FDA for our Phase II CO ARDS trial (NCT03799874).

Patients with hemoglobin < 7.0 g/dL, Jehovah's witnesses, or patients otherwise unable or unwilling to receive blood transfusions during hospitalization are excluded because of the volume of blood drawn for monitoring during iCO therapy may place these patients at greater risks from complications of anemia. Moribund patients and patients with extensive body surface area burns have a high incidence of AEs and lactic acidosis that will confound the safety assessment. Pregnancy, recent stroke, or cardiac arrest are exclusions because iCO may reduce oxygen delivery to the fetus and recently injured brain respectively. Patients with alveolar hemorrhage from vasculitis are excluded because the mechanism of lung injury is

different from ARDS and diffuse alveolar damage. Patients with acute MI within 90 days, recent CABG, and angina pectoris are excluded because of a potential excess risk of reducing oxygen delivery to the myocardium. Patients with NYHA class IV cardiopulmonary disease are excluded because of concerns about ventricular arrhythmias and high mortality. Patients ventilated with high frequency oscillatory ventilation are excluded because administration of iCO with this mode of ventilation may be potentially unreliable. Patients on ECMO are also excluded because the effects of CO uptake and elimination from the blood during ECMO are unknown. Patients on concurrent inhaled pulmonary vasodilator therapy are excluded as these inhaled medications may interfere with the dosing of iCO.

Patients who are cigarette smokers, but otherwise eligible for inclusion, will not be excluded from potential enrollment in the study. Rather, enrolled subjects will be screened with daily COHb levels and study drug treatment held if COHb $\geq 3\%$. This criterion was implemented for our Phase Ia study and will be used in this trial as smoking history obtained from surrogate decision makers may be unreliable and the average COHb half life is 240 minutes when breathing room air and less on supplemental oxygen¹³⁴⁻¹³⁶.

Exclusion on the basis of smoking history would preclude many patients from receiving this potentially beneficial treatment. Instead, this protocol incorporates treatment holds on the basis of daily COHb levels, which will allow otherwise eligible patients to be treated safely and have the opportunity to benefit from this potentially new promising therapy. We anticipate enrolling smokers at a frequency similar to their proportion in our target populations.

